#### 4.1 Criteria for Removal from Study

Subjects MUST discontinue study treatment by cancelling the tilmanocept injection and SPECT/CT scan for any of the following reasons:

- Withdrawal of informed consent (subject's decision to withdraw for any reason).
- Any clinical AE, laboratory abnormality, or intercurrent illness that, in the opinion of the investigator, indicates that continued participation in the study is not in the best interest of the subject.
- Discovery of metastatic disease in the operating room.
- Pregnancy.
- Loss of ability to freely provide consent through imprisonment or involuntary incarceration for treatment of either a psychiatric or physical (e.g., infectious disease) illness.

All subjects who discontinue study treatment should comply with protocol-specified follow-up procedures as outlined in Section 7.2. The only exception to this requirement is when a subject withdraws consent for all study procedures or loses the ability to consent freely (i.e., is imprisoned or involuntarily incarcerated for the treatment of either a psychiatric or physical illness). If a subject was withdrawn before completing the study, the reason for withdrawal must be entered on the appropriate case report form (CRF) page.

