	sentinel lymph nodes using near infrared imaging and the gamma probe.
SAMPLE SIZE	30 patients over 1 year
STATISTICAL CONSIDERATIONS	
The analysis population will include all patients who complete the study procedures specified above. We do not expect missing data or loss-to-follow up since the outcome is ascertained at the time of surgery. Patients who do not adhere to the study treatment plan of both injections, SPECT/CT and surgery with sentinel lymph node assessment will not be included in the analysis population.
 
To address our primary objective, we plan to enroll 30 patients with concurrent use of lymphoseek and indocyanine green over 1 year. The primary analysis is the calculation of the bilateral SLN detection rate which will be calculated as the number of patients with bilateral SLN detection divided by the total number of patients.
 
With 30 participants and assuming a true bilateral detection rate of 80%, the probability of correctly concluding that our approach has an acceptable bilateral detection rate (i.e., 24 patients being detected with bilateral SLNs) is 61%. The probability of incorrectly concluding this (assuming that the true detection rate is 69%) is low at 13%. We will deem the approach used in this study promising if we observe a bilateral detection rate of at least 80%.

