## **4. TREATMENT PLAN**

In this study, the patient will receive cervical injections of Lymphoseek 1 – 24 hours prior to surgery and subsequent SPECT/CT imaging preoperatively. Intraoperatively, following anesthesia induction, Indocyanine Green will be injected into the uterine cervix. Using near-infrared imaging, efferent lymphatic vessels and lymph nodes will be visualized and confirmed by detected radioactivity using a laparoscopic gamma counter. The preoperatively obtained SPECT/CT images will help guide the surgery. The laparoscopic gamma counter will confirm that sentinel lymph node tissue was removed by recording gamma counts before and after lymph node removal.

Subject participation in this study comprises the following:

- Screening**

- Screening begins after informed consent is obtained.
- The screening window is Day 1 to Day 42 after signing of informed consent.
- Screening assesses the subject's eligibility to participate as determined by inclusion/ exclusion criteria.

- Sentinel lymph node assessment**

- Preoperatively, 1 - 24 hrs prior to surgery, the patient will receive in the nuclear medicine suite of Stanford Hospital injections of 0.125 mCi or 0.5 mCi mL each Lymphoseek into the uterine cervix at 3, 6, 9, and 12 o'clock. Then, the patient will undergo SPECT/ CT imaging. Immediate and delayed static planar images will be obtained with and without a transmission source. SPECT-CT of the abdomen and pelvis will be obtained for further characterization. The imaging process will take approximately 1 hour.

- The patient will undergo minimally invasive endometrial cancer surgery. The SPECT/ CT images will be available for review to the surgeon prior to the start of the surgery.
- In the operating room, following anesthesia induction, the uterine cervix of the patient will be injected with about 2.0 mL total of Indocyanine Green. The surgery will start with the identification and dissection of sentinel lymph nodes.
- **Follow up (duration of the study)**
  - The patient will be observed preoperatively after Lymphoseek injection in the nuclear medicine suite and postoperatively in the recovery room for possible allergic reactions or any other adverse events.

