### **11.4 Primary Analysis**

#### **11.4.1. Analysis Population**

The analysis population will include all patients who complete the study procedures specified above. We do not expect missing data or loss-to-follow up since the outcome is ascertained at the time of surgery. Patients who do not adhere to the study treatment plan of both injections, SPECT/CT and surgery will not be included in the analysis.

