## **11.5. Secondary Analysis**

### **11.5.1 Analysis Population**

The population for secondary analysis will include all patients in the safety population, i.e. the analysis population plus those women who underwent lymphoseek injection but were removed from the study for any reason.

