### **11.5.2 Analysis Plan**

Descriptive statistics will be used to analyze the secondary outcomes. The overall detection rate of sentinel lymph nodes will be calculated as the number of patients with overall SLN detection divided by the total number of patients. To assess the safety of the concurrent use Lymphoseek and Indocyanine Green, we will calculate the number and rate of adverse events. We will describe the location and number of Lymphoseek-positive SLNs by method of detection (pre-operative or intraoperative). We will calculate the number of patients with SLNs found by Lymphoseek and by Indocyanine Green and conduct a McNemar's test (or mid- $p$  McNemar's test) to determine the concordance of Lymphoseek-positive and Indocyanine Green-positive sentinel lymph nodes.

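### Section 11.5.1 puts overall detection and tracer concordance on the safety population, which can include women never assessed with Indocyanine Green

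*Combined protocol and SAP*

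**What the plan says.** Section 4 fixes the order of events: "the patient will receive cervical injections of Lymphoseek 1 – 24 hours prior to surgery and subsequent SPECT/CT imaging preoperatively". Indocyanine Green follows after induction of anesthesia, and "The surgery will start with the identification and dissection of sentinel lymph nodes".

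Section 4.1 lists the reasons for removal under the lead-in "Subjects MUST discontinue study treatment by cancelling the tilmanocept injection and SPECT/CT scan for any of the following reasons". One of them is "Discovery of metastatic disease in the operating room". Others, such as withdrawal of consent or an adverse event, can arise between the Lymphoseek injection and surgery.

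For the primary analysis, Section 11.4.1 states: "The analysis population will include all patients who complete the study procedures specified above". The synopsis adds that patients who do not adhere to "both injections, SPECT/CT and surgery with sentinel lymph node assessment will not be included in the analysis population".

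For the secondary analyses, Section 11.5.1 uses the safety population, defined as "the analysis population plus those women who underwent lymphoseek injection but were removed from the study for any reason". Section 11.5.2 then lists what is analysed: "The overall detection rate of sentinel lymph nodes will be calculated as the number of patients with overall SLN detection", over the total number of patients; adverse events; the location and number of Lymphoseek-positive nodes by method of detection; and a McNemar test of Lymphoseek against Indocyanine Green.

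**The concern.** A safety population is right for adverse events, because every woman exposed to Lymphoseek is at risk of one. It is the wrong set for a detection rate or a paired comparison of two tracers, because some of its members were never assessed with one of them.

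Three results are affected:

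- **Overall detection.** On one set of women, the overall rate minus the bilateral rate is the share with detection on one side only. With two sets that subtraction no longer holds.
- **Tracer comparison.** A woman imaged by SPECT/CT and then removed can be positive for Lymphoseek but has no Indocyanine Green result. If the missing result counts as negative, she is evidence for Lymphoseek that nobody observed.
- **Location and number of nodes.** Such a woman adds to the preoperative count but cannot add to the intraoperative one.

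**Working it through.** **The plan's own figures.** With 30 women and a cut-off of 24, the exact binomial probability of 24 or more is 0.607 at a true rate of 80% and 0.133 at 69%. The exact 95% interval for 24/30 is 61.4% to 92.3%. These agree with the stated 61%, 13% and 61% to 92%. They concern the bilateral rate, which this point leaves unchanged.

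**Who enters under 11.5.1.** Three cases, read against Sections 4, 4.1, 11.4.1 and the synopsis:

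1. Removed after Lymphoseek and before anesthesia: no Indocyanine Green and no node assessment. Outside the primary population, inside the secondary one.
2. Metastatic disease found at surgery before node assessment: Indocyanine Green has probably been given, since it follows induction, but there is no near-infrared or gamma-probe result. Outside the primary population by the synopsis wording, inside the secondary one.
3. Metastatic disease found after mapping is finished: all procedures completed. Inside the primary population by the opening sentence of 11.4.1, and inside the secondary one.

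Cases 1 and 2 cause the problem.

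**Denominators.** The documents give no frequency. Assume, for scale only, that 30 women are injected, k of them fall in case 1 or 2 (k = 0, 1 or 2), and none is replaced. The bilateral rate has denominator 30 − k and the overall rate has 30: that is 30 and 30, 29 and 30, or 28 and 30.

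**Overall rate.** Let x of the 30 − k completers have any node detected. Among completers the rate is x/(30 − k). Under 11.5.1 it lies between x/30 (no removed woman positive on SPECT/CT) and (x + k)/30 (all positive). Take x near the 88% overall rate that Section 2.1 reports for Indocyanine Green at the institution:

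- k = 1: 0.88 × 29 = 25.5, so x = 26. Completers 26/29 = 89.7%; under 11.5.1, 26/30 = 86.7% to 27/30 = 90.0%.
- k = 2: 0.88 × 28 = 24.6, so x = 25. Completers 25/28 = 89.3%; under 11.5.1, 25/30 = 83.3% to 27/30 = 90.0%.
- k = 0: no change.

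**Paired comparison.** Let b be the women positive for Lymphoseek only and c those positive for Indocyanine Green only. The paired difference among completers is (b − c)/(30 − k). A removed woman with a positive SPECT/CT, scored negative for Indocyanine Green, adds 1 to b and never to c. If all k are of this kind, the difference becomes (b + k − c)/30. When the tracers perform equally among completers (b = c), it moves from 0 to 1/30 = 3.3 points for k = 1, or 2/30 = 6.7 points for k = 2. A removed woman with no positive SPECT/CT is negative for both and leaves b and c unchanged.

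Spurious pairs alone would not make the test significant. With b = c = 0 among completers and k = 2, the split is 2 to 0: the exact two-sided p-value is 2 × (1/2)² = 0.50, and the mid-p value is 0.50 − 0.25 = 0.25. Where real discordant pairs already favour Lymphoseek, the added pairs push the p-value down by an amount that depends on counts the documents do not give.

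**The case against.** The best defence is that nobody would run it this way. A McNemar test needs two results per woman, so an analyst would drop a woman with no Indocyanine Green result, and 11.5.1 may have been written with adverse events in mind. That is plausible, and it limits the harm. But 11.5.1 names its population for the secondary analysis without qualification, and 11.5.2 has no rule for an untested tracer. Dropping her would depart from the stated population.

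A second defence is that counting every injected woman is a legitimate way to judge a procedure, since a woman who never reaches mapping gains nothing from it. That would be coherent if the bilateral rate used the same set. It does not.

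It also stands that the frequency is unknown, the study is a feasibility study, and its analysis is mainly descriptive.

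A reader might infer something stronger: that 4.1 and 11.5.1 together expel a fully mapped woman from the primary population when metastatic disease is found, contradicting 11.4.1 and putting the 'promising' call at risk. The documents do not support this. Section 11.5.1 defines only the secondary population, and its 'plus' can describe a union whose two parts overlap. The express rule is in 11.4.1, and it keeps completers. One can construct reversals, such as 24/30 = 80.0% against 23/29 = 79.3%, but those are results chosen at the cut-off, and the documents give neither frequency nor direction for the event. The lower power at 29 women (46.3%, against 60.7% at 30) is largely the step in the cut-off: it is 50.1% at 28 and 53.9% at 27.

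The cancellation wording in 4.1 is a real slip, because injection and scan precede the operating room. By itself it changes no result.

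**Conclusion.** The population in 11.5.1 is wrong as written for overall detection, node location and number, and concordance. It is right for adverse events. Severity is minor.

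The mismatch in populations follows from the text alone. Its size rests on assumptions: zero to two removed women among 30 injected, none replaced, and an untested tracer scored as negative. On those assumptions the overall rate could fall by up to 6.0 points (89.3% to 83.3%) or rise by up to 0.7 (89.3% to 90.0%), and equal tracers could appear to differ by up to 6.7 points. With no such women there is no effect. No effect on the primary result is shown.

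**What to change.** **Main change, Section 11.5.1.** Use the 11.4.1 analysis population for overall detection, node location and number, and concordance. Keep the safety population for adverse events only. List removed women with the reason.

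**Two clarifications to go with it.**

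- In 11.4.1, with the synopsis aligned, state that women who received both injections and SPECT/CT, and in whom sentinel node assessment was attempted, stay in the primary denominator whatever is found at surgery, scored by 9.1. Do not exclude a woman because assessment stopped before both sides were examined. Under 9.1 detection on SPECT/CT alone counts, so she may already have a result, and such an exclusion could let mapping failures leave the denominator.
- In 4.1, limit the cancellation wording to reasons that arise before the Lymphoseek injection.

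**Cost.** Wording in four places, with no extra patients, procedures or data; 4.1 already requires the withdrawal reason on the case report form. The downside is that secondary detection results omit the few injected women who did not complete the procedures, which the listing makes visible. The primary denominator may also include a few women whose disease proves not to be confined to the uterus.

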#### 4.2 Alternatives

Injection with Indocyanine Green alone for sentinel lymph node mapping and biopsy in clinical uterine confined endometrial cancer is currently considered standard of care.

## 5. INVESTIGATIONAL AGENTS

### 5.1 Lymphoseek

Kit for the preparation of Lymphoseek contains five Tilmanocept Powder vials, each contain 250 mcg of tilmanocept from which 50 mcg is intended for administration to a patient.

#### 5.1.1 Handling and dispensing of Lymphoseek

Lymphoseek must be stored in a secure area according to local regulations. It must be stored in the original packaging at controlled room temperature 20-25° C, excursions permitted to 15-30° C. Radiolabeled Lymphoseek must be stored in radiation shielding at room temperature and used within 6 hours of preparation.

Waterproof gloves, effective radiation shielding, and appropriate safety measures will be used when preparing and handling Lymphoseek. As a radiopharmaceutical Lymphoseek will be used under the control of physicians who are qualified by specific training and experience in the safe use and handling of radionuclides, and whose experience and training have been approved by the appropriate governmental agency authorized to license the use of radionuclides.

#### 5.1.2 Preparation and administration of Lymphoseek

Each patient will receive 4 injections of 0.125 mCi into the cervix at the 12, 3, 6, and 9 o'clock positions for the same day of surgery (0.125 mCi x 4 or 0.5 mCi +/- 20%) for the same day of surgery.

Each patient will receive 4 injections of 0.5 mCi into the cervix at 12, 3, 6, and 9 o' clock positions for the next day surgery (0.5 mCi x 4 or 2.0 mCi +/- 20%) for the next day of surgery.

As per manufacturer's instructions, the reconstitution volume will be 2.5 mL.

#### Radiolabeling

Technetium Tc 99m pertechnetate, the sodium injection solution from a technetium Tc 99m generator within 8 hours of its elution will be used. Using a sterile syringe, approximately 92.5 MBq (2.5 mCi) of Technetium Tc 99m pertechnetate sodium injection solution will be drawn in 0.7 mL volume. The syringe will be assayed for technetium Tc 99m activity in a dose calibrator. The radioactivity amount, the vial volume, date and time, expiration time and lot number will be written on the radioactive product vial label and affixed to the Tilmanocept Powder vial. The vial will be placed in a radiation shield, the septum sanitized with an alcohol wipe.

Under aseptic conditions the Technetium Tc 99m pertechnetate sodium injection solution will be added to the Tilmanocept Powder vial. Without withdrawing the needle, an equal volume of headspace gas will be removed. After removing the needle, the vial will be gently shaken to mix contents and then incubated at room temperature for at least 15 minutes.

#### Reconstitution

Then, the supplied DILUENT for Lymphoseek will be added aseptically to the radiolabeled product in the Tilmanocept Powder vial to bring the volume to the reconstituted vial volume of 2.5 mL prior to filling the patient dose in syringe(s). To normalize pressure, withdraw an equal volume of headspace gas.

For quality control, the reconstituted vial will be assayed for total radioactivity using a dose calibrator. The activity of the syringes will be assayed in the dose calibrator before application to the patient.

#### Physical Characteristics

Technetium Tc 99m decays by isomeric transition with a half-life of approximately 6 hours. The principal photon that is useful for detection and imaging studies is Gamma-2 with a mean energy of 140.5 keV and a mean disintegration of 89.1%.

#### External Radiation

The linear mass energy absorption attenuation coefficient for Tc 99m is 18.9 cm^-1. The first half-value layer is 0.037 cm of lead (Pb). The use of a 0.25 cm thick standard radiation lead shield will attenuate the radiation emitted by millicurie amounts of technetium Tc 99m by a factor of about 100. The half-life of technetium Tc 99m is approximately six hours.

## **5.2 Indocyanine Green**

Indocyanine Green (IC-GREEN®) is a sterile, lyophilized green powder containing 25 mg of Indocyanine Green with no more than 5% sodium iodide. Indocyanine Green (IC-GREEN®) is supplied in a kit containing six 25-mg Indocyanine Green (IC-GREEN®) vials and six 10-mL sterile water for injection, USP ampules.

### **5.2.1 Handling and dispensing of Indocyanine Green**

As with all injectable drugs, care should be taken when handling and preparing Indocyanine Green. Whenever possible, it should be prepared in a laminar flow hood or safety cabinet using standard precautions for the safe handling of injectable agents, applying aseptic technique.

The Indocyanine Green (IC-GREEN®) powder should be dissolved with the sterile water for injection, USP provided and the solution should be used within 6 hours after it is prepared. The Indocyanine Green (IC-GREEN®) kit will be stored at 20-25°C.

### **5.2.2 Preparation and administration of Indocyanine Green**

Cervical injection by the investigator of 0.5 mL each of the 0.5 mg/mL Indocyanine Green solution at 12, 3, 6, and 9 o'clock follows anesthesia induction.

## **5.3 Availability**

Lymphoseek will be provided already reconstituted and radiolabeled by outside pharmacy. Indocyanine Green (IC-GREEN ®) will be provided by the Pharmacy of Stanford Hospital and

prepared in the operating room by the registered nurse in the usual fashion.

## **6. DOSE MODIFICATIONS**

There will not be any dose modifications for either Lymphoseek or Indocyanine Green. If anaphylactic or urticarial reactions occur, the patient will be treated with the appropriate agents, e.g. epinephrine, antihistamines, and corticosteroids.

## **7. ADVERSE EVENTS AND REPORTING PROCEDURES**

### **7.1 Potential Adverse Events**

#### **7.1.1 Potential Adverse Events associated with Lymphoseek**

The most common adverse reactions (incidence <1%) are injection site irritation and/or pain. In open label, single-arm clinical trials, 553 patients with either breast cancer, melanoma, or squamous cell carcinoma of the oral cavity, skin, lip received Lymphoseek. No patient experienced serious adverse reaction. Injection site irritation (0.7%) and pain (0.2%) were reported [29].

Lymphoseek may pose a risk of hypersensitivity reactions due to its chemical similarity to dextran. No hypersensitivity reactions have been reported in the literature.

#### **7.1.1.1 Radiation Risks with Lymphoseek**

Any radiation-emitting product may increase the risk for cancer. Adherence to dose recommendations and safe handling will minimize the risk of excessive radiation exposure to either patients or health care workers which includes the radiation exposure in the operating room (OR). No additional protection for the OR staff is required.

#### **7.1.2 Potential Adverse Events associated with Indocyanine Green**

Most common adverse reactions are anaphylactic or urticarial reactions. They have been reported in patients with and without history of allergy to iodine. If such reactions occur, the patient will be treated with the appropriate agents, e.g. epinephrine, antihistamines, and corticosteroids. In breast cancer and melanoma, extensive information on Lymphoseek's safety exist but we will continue to monitor and report its safety in this population. Monitoring for adverse events to Lymphoseek will start after its injection into the uterine cervix.

### **7.2 Adverse Event Reporting**

Adverse events will be graded according to CTCAE v4.03. Both Serious and Non-Serious Adverse Events will be clearly noted in source documentation and listed on study specific Case Report Forms (CRFs). The Protocol Director (PD) or designee will assess each Adverse Event (AE) to determine whether it is unexpected according to the Informed Consent,

Protocol Document, or Investigator's Brochure, and related to the investigation. All Serious Adverse Events (SAEs) will be tracked until resolution, or until 30 after the last dose of the study treatment.

SAEs CTCAE Grade 3 and above, and all subsequent follow-up reports will be reported to the Stanford Cancer Institute Data and Safety Monitoring Committee (DSMC) using the study specific CRF regardless of the event's relatedness to the investigation. Following review by the DSMC, events meeting the IRB definition of 'Unanticipated Problem' will be reported to the IRB using eProtocol within 10 working days of DSMC review, or within 5 working days for deaths or life-threatening experiences.

